2.6. Site Pooling

Analysis centers will be created by totaling the number of subjects at each site and pooling smaller sites together.

Sites with fewer than 8 subjects will be pooled. Sites will be sorted by country, the number of subjects at that site in descending order, and then site number in ascending order. For each country separately, the site at the top of the list (the largest site with less than 8 subjects and, if tied, the smallest site number) will be pooled with the site at the bottom of the list (the smallest site with less than 8 subjects and, if tied, the largest site number). If the pooled site now has at least 8 subjects, it is removed from the list.

Otherwise, it will continue to be combined with the smallest available site until it has at least 8 subjects or no sites remain.

After all possible pooling is done, if all remaining small sites cannot be pooled together into an analysis center with at least 8 subjects, those sites will all be pooled into the analysis center created in the previous iteration of the pooling, even if that analysis center is not the smallest. If there was no other pooling done (because all small sites in the country total to less than 8 subjects), those sites will be pooled with the smallest site in the country. If no other sites are available in that country, the site will remain with fewer than 8 subjects.

3. Protocol Deviations

Protocol deviations will be provided in the DV SDTM dataset. Subjects with a deviation categorized as "Major" or "Major for face" will be excluded from the PP population. Subjects with a deviation categorized as "Major," "Major for face," or "Major for trunk" will be excluded from the PPT population.

The number of subjects in each analysis population will be summarized, and specific protocol deviations will be summarized in a listing.

4. Disposition

For the purposes of disposition summaries, subjects are considered to be Screened if they have signed the Informed Consent form. Subjects will be considered randomized once they've been assigned a treatment.

5. Prohibited Medications

Prohibited medications will be flagged on the concomitant medications listing. A list of prohibited medications with ATC/Drug names will be identified prior to the database lock.

6. Efficacy Analyses

6.1. IGA/PGA Success Rate

Success rate of IGA and PGA will be calculated for each visit. Success rate will be calculated as the number of subjects considered a success at that visit divided by the number of subjects with IGA/PGA data at that visit.

The large-sample approximation for binary data will be used for the 95% confidence intervals around the difference in success rates. Continuity corrections will not be used for either the CMH test or the generation of 95% confidence intervals.

The success rate of IGA and PGA using missing data procedures will be presented at Week 12. The success rate of IGA and PGA will be presented at each visit using the observed data; no missing data imputation will be used.

In addition, overall success rate at Week 12 will be calculated using missing data procedures assuming that the data is missing at random. Overall success rate at Week 12 is defined as having an IGA score of

“clear” or “almost clear” at Week 12 and a grade change of at least two from baseline and having a PGA score of “clear” or “almost clear” at Week 12 and a grade change of at least two from baseline.

6.2. Multiple Imputation – Missing at Random

A multiple imputation method will be used to account for missing data on efficacy analyses. The following steps will be followed:

- 1) For lesion counts, the pattern of missingness in the data will be evaluated. If the data is not monotone missing, the MCMC method will be used to make it monotone missing. The single chain method will be used, with 200 burn-in iterations and 100 iterations between imputations. Fifty imputations will be created. The seed number will be 18251. Lesion counts generated as a result of the MCMC method will be re-imputed if they are below zero; they will not be rounded.
- 2) The MI procedure in SAS will be used to create multiple imputations of the data that have no missing values. If the MCMC method was previously employed, one imputation will be made using each of the fifty MCMC-imputed datasets. If the MCMC method was not used, fifty imputations will be created using the MI procedure assuming the data is Missing at Random. The seed number will be 18251. These imputations will use the following models:
 - a. For IGA and PGA scores, a logistic regression model will be used with covariates for treatment and non-missing data from earlier scheduled time points including baseline. Weeks will be imputed sequentially, with IGA/PGA data at prior non-baseline weeks treated as continuous data (baseline will be treated as categorical).
 - b. For lesion counts, a linear regression model will be used with covariates for treatment and non-missing data from earlier scheduled time points including baseline.
- 3) The imputed datasets will be analyzed as follows:
 - a. For IGA and PGA scores, the number of successes at Week 12 will be analyzed using the CMH test stratified by analysis center. The sample difference in proportions and its standard error will also be calculated. No continuity corrections will be used.
 - b. For lesion counts, change from baseline to Week 12 in lesion counts will be analyzed using an ANCOVA model with covariates for baseline count, analysis center, and treatment.
- 4) The resulting analysis on the imputed datasets will then be combined to produce a single set of statistics.
 - a. For IGA and PGA scores, the results from the CMH analysis will be combined using the procedure by Rubin (1987) and Li et al. (1991) to produce a pooled CMH statistic and p-value. The differences in proportions and standard errors will be combined using the MIANALYZE procedure in SAS; the resulting pooled difference and standard errors will be used to produce 95% confidence intervals based on the large-sample approximation method for binary data without the use of a continuity correction. Both methods will be used as described in the Bohdana Ratitch et al. paper *Combining Analysis Results from Multiply Imputed Categorical Data*.
 - b. For lesion counts, results from the ANCOVA analysis will be combined using MIANALYZE procedure in SAS.

Below is an example of the SAS syntax for the logistic MI procedures for IGA/PGA:

```
proc mi data=transI seed=18251 out=miI1 nimpute=50 noprint;
class trt01pn baseline week_1;
var trt01pn baseline week_1;
monotone logistic(week_1=trt01pn baseline);
run;

proc mi data=miI1 seed=18251 out=miI2 nimpute=1 noprint;
by _IMPUTATION_;
class trt01pn baseline week_2;
var trt01pn baseline week_1 week_2;
monotone logistic(week_2=trt01pn baseline week_1);
run;

proc mi data=miI2 seed=18251 out=miI3 nimpute=1 noprint;
by _IMPUTATION_;
class trt01pn baseline week_4;
var trt01pn baseline week_1 week_2 week_4;
monotone logistic(week_4=trt01pn baseline week_1 week_2);
run;

proc mi data=miI3 seed=18251 out=miI4 nimpute=1 noprint;
by _IMPUTATION_;
class trt01pn baseline week_8;
var trt01pn baseline week_1 week_2 week_4 week_8;
monotone logistic(week_8=trt01pn baseline week_1 week_2 week_4);
run;

proc mi data=miI4 seed=18251 out=miI(rename=_imputation_=imp) nimpute=1
noprint;
by _IMPUTATION_;
class trt01pn baseline week_12;
var trt01pn baseline week_1 week_2 week_4 week_8 week_12;
monotone logistic(week_12=trt01pn baseline week_1 week_2 week_4 week_8);
run;
```

Below is an example of the SAS syntax for the MCMC and linear MI procedures for lesion counts:

```
proc mi data=transI seed=18251 out=mcmcI(rename=_imputation_=imp) nimpute=50
minimum=0 noprint;
mcmc impute=monotone chain=single nbiter=200 niter=100;
var baseline week_1 week_2 week_4 week_8 week_12;
run;

proc mi data=mcmcI seed=18251 out=miI nimpute=1 minimum=. 0 0 0 0 0 0
noprint;
by imp;
class trt01pn;
var trt01pn baseline week_1 week_2 week_4 week_8 week_12;
monotone reg(week_12=trt01pn baseline week_1 week_2 week_4 week_8);
run;
```

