A Multi-Center, Randomized, Double-Blind, Parallel-Group Vehicle Controlled Study To Compare The Efficacy And Safety Of CD5789 50µg/g Cream Versus Vehicle Cream In Subjects With Acne Vulgaris

RD.06.SPR.18251

EUDRACT NUMBER : 2016-002860-15

IND NUMBER : 111091

1/ CLINICAL TRIAL OBJECTIVES

The clinical trial objectives are to assess the efficacy and safety of CD5789 50 µg/g cream applied once daily for 12 weeks in subjects with moderate facial and truncal acne vulgaris.

2/ STUDY DESIGN

Phase 3, multi-center, randomized, double blind, vehicle controlled study comparing CD5789 cream applied once daily in the evening for 12 weeks versus its vehicle.

Group 1: CD5789 50µg/g cream

Group 2: Vehicle cream

Subjects treated once daily for 12 weeks and evaluated at Baseline, Weeks 1, 2, 4, 8 and 12/Early Termination.

3/ CLINICAL STUDY DURATION

The planned clinical trial duration (from FSI to LSO) is approximately 26 months.

The planned duration of recruitment (i.e. From FSI to LSI) is approximately 23 months.

4/ DURATION OF SUBJECT PARTICIPATION & SUBJECTS' VISITS

Clinical trial participation for each subject is approximately 14 weeks (screening period of 14 days with a time window of + 3 days followed by 12 weeks of study treatment ±5 days).

5/ TOTAL NUMBER OF SUBJECTS (PLANNED):

Approximately 1500 subjects will be screened in order to obtain 1200 randomized subjects (600 per treatment arm).

6/NUMBER OF CLINICAL TRIAL CENTERS (PLANNED):

Approximately 160 sites

7/ REGION(S) / COUNTRY(IES) INVOLVED (PLANNED):

United States, Puerto Rico, Europe, Canada and Russia

8/ INCLUSION/EXCLUSION CRITERIA

8.1/ Inclusion criteria:

1. The subject is a male or female, 9 years of age and older at the Screening visit.
For Russia : The subject is a male or female, 9-17 years of age OR 18 years and older, at Screening visit

2. The subject has a facial acne severity grade of 3 (moderate) on the Investigator Global Assessment (IGA) scale at Screening and Baseline.
3. The subject has a minimum of 20 inflammatory lesions and 25 non-inflammatory lesions on the face at Screening and Baseline.
4. The subject has a truncal acne severity grade of 3 (moderate) on the Physician Global assessment (PGA) scale at Screening and Baseline visits on trunk (shoulders, upper back and upper anterior chest) reachable for self-application of study drug by the subject (optional criterion for subject between 9 and 11 years of age).

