6.4. Multiple Imputation – Categorical Sensitivity Analysis

The primary multiple imputation method will treat IGA/PGA as continuous when used as covariates for the logistic regression model. As a sensitivity analysis, the multiple imputation process for IGA/PGA will be repeated treating those predictors as categorical.

First, the pattern of missingness in the data will be evaluated. If the data is not monotone missing, the MCMC method will be used to make it monotone missing. The single chain method will be used, with 200 burn-in iterations and 100 iterations between imputations. Fifty imputations will be created. If all subjects have the same baseline IGA/PGA value, the baseline visit will not be included in the model. The seed number will be 18251. IGA and PGA scores generated as a result of the MCMC method will be rounded prior to the next step; scores will be re-imputed if, after rounding, they are lower than 0 or higher than 4.

Due to the categorical nature of the data, and the rarity of some values of IGA/PGA, there is the potential for convergence issues when using logistic regression with categorical covariates. If this is the case, each week will be imputed sequentially and predictor weeks that cause convergence issues (and thus can't be used as valid predictors) will be dropped.

The model will be chosen by first checking if the inclusion of any covariates causes convergence issues. If so, predictor weeks will be removed from the model and the model rerun until any convergence issues are solved. Earlier weeks will be dropped from the model before later weeks, and combinations of weeks will only be dropped if the removal of only one week does not cause the model to converge. Thus, weeks will be dropped in the following order:

1. Week 1
2. Week 2
3. Week 4
4. Week 8
5. Weeks 1 and 2

6. Weeks 1 and 4
7. Weeks 2 and 4
8. Weeks 1 and 8
9. Weeks 2 and 8
10. Weeks 4 and 8
11. Weeks 1, 2, and 4
12. Weeks 1, 2, and 8
13. Weeks 2, 4, and 8

After each removal, the model will be rerun. The first model that converges will be kept, and the process will restart with the next week until Week 12 is imputed. The final chosen models will be run with seed number 18251. Below is an example of the SAS syntax for the MCMC and logistic MI procedures treating predictor weeks as categorical, with no weeks removed:

```
proc mi data=transI seed=18251 out=mcmcI(rename=_imputation_=imp) nimpute=50
minimum=0 maximum=4 round=1;

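### The IGA/PGA imputation models use only prior scores, whose baseline value eligibility fixes at 3, and leave out the baseline lesion counts

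*SAP*

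**What the plan says.** Protocol inclusion criterion 2 requires a "facial acne severity grade of 3 (moderate) on the Investigator Global Assessment (IGA) scale at Screening and Baseline". Criterion 4 sets the same grade for truncal PGA. It is optional at ages 9 to 11, but SAP section 5.2 excludes children who do not meet it from the ITTT population. Facial lesion counts have only a lower limit at entry (criterion 3): "The subject has a minimum of 20 inflammatory lesions and 25 non-inflammatory lesions on the face at Screening and Baseline".

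The primary imputation for IGA and PGA is in SAP addendum section 6.2: "a logistic regression model will be used with covariates for treatment and non-missing data from earlier scheduled time points including baseline". The next sentence describes how the earlier data enter: "with IGA/PGA data at prior non-baseline weeks treated as continuous data (baseline will be treated as categorical". The example code begins with "monotone logistic(week_1=trt01pn baseline" and ends with "monotone logistic(week_12=trt01pn baseline week_1 week_2 week_4 week_8". None of its five weekly steps contains a lesion count. Section 6.3 drops treatment from the regressions, fits them to vehicle subjects, and has no counts either.

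Section 6.4, a sensitivity analysis, contains a rule that 6.2 and 6.3 lack: "If all subjects have the same baseline IGA/PGA value, the baseline visit will not be included in the model".

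**The concern.** A missing-at-random imputation is only as credible as the covariates it conditions on. Here the one baseline covariate is nearly constant by design. The baseline severity measures that do vary, the inflammatory and non-inflammatory counts, are scheduled at Baseline but not used. Elsewhere the plan treats them as prognostic: the lesion-count ANCOVA adjusts for the baseline count and its interaction with treatment is examined (SAP 7.4.1.1 and 7.4.2.1).

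IGA success is one of three co-primary endpoints that must all be significant. It is tested by a CMH test stratified by analysis center only, so nothing later in the analysis makes up for the omission. If dropout depends on how heavy the acne was at entry, and differently in the two arms, the imputed success rates could shift the treatment difference.

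**Working it through.** **1. The plan's own figure.** SAP section 6 assumes success of 23% v 15%, 90% power, two-sided 0.05 and 16% loss. With pooled variance and no continuity correction, and a mean rate of 0.19:

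n = [1.960 × √(2 × 0.19 × 0.81) + 1.282 × √(0.23 × 0.77 + 0.15 × 0.85)]² / 0.08² = 503.3, so 504 per arm; 504 / 0.84 = 600.

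Both figures are reproduced. The imputation covariates do not enter them.

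**2. What the model reduces to.** With baseline IGA = 3 for everyone, the Week 1 design matrix (intercept, treatment, baseline) has 3 columns and rank 2, so only treatment remains. For a subject with no post-baseline IGA, each later week is imputed from weeks that were themselves imputed from arm. In 6.3 the Week 1 regression on baseline alone becomes a draw from the vehicle distribution with no subject-level covariate.

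**3. Early losses, by hand.** The documents do not say how many subjects will have no post-baseline score, so let a share e of each arm be lost this early (assumption). Arm-only imputation gives them about 23% and 15% success. If their true rates are r_A and r_V times the arm's rate, the difference is overstated by e × [0.23(1 − r_A) − 0.15(1 − r_V)].

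| e | Lost per arm | Imputed successes, active / vehicle | Overstatement, r_A = 0.5, r_V = 1 | Overstatement, both 0.5 |
|---|---|---|---|---|
| 1% | 6 | 1.4 / 0.9 | 0.1 points | 0.04 points |
| 4% | 24 | 5.5 / 3.6 | 0.5 | 0.16 |
| 8% | 48 | 11.0 / 7.2 | 0.9 | 0.32 |
| 16% | 96 | 22.1 / 14.4 | 1.8 | 0.64 |

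With r_A = r_V = 1 the overstatement is zero. The last row is a ceiling: all planned loss would have to fall before the first post-baseline score. Halving is an illustration, not an estimate.

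**4. Dropout driven by the baseline count.** Assume log-odds of success fall by 0.3 to 0.6 per SD of count and log-odds of early loss rise by 0.5 per SD (odds ratio 1.65), with all losses imputed from arm alone. If the dependence is in the active arm only, the overstatement is 0.06 to 0.08 points at 2% early loss, 0.13 to 0.23 at 5% and 0.40 to 0.76 at 16%. If it is equal in both arms, it is at most 0.19 points, reached at 16%.

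**5. The full weekly sequence.** This was simulated with sequential proportional-odds imputation, 23% v 15% and 16% missing. Assumptions: count correlated 0.3 to 0.5 with severity, and 10 to 40% of dropouts with no post-baseline score.

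- Active-arm-only dependence, odds ratio 2 per SD: roughly 0.4 to 1.0 points in favour of active. At odds ratio 1.5 it was about 0.45. With the counts in the model, the remaining error was 0.0 to 0.15, within simulation noise.
- Equal dependence in both arms: about 0.1 to 0.3 points.
- No dependence: none.

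The shift persisted when only 10% of dropouts were that early, so later dropouts are affected too.

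**6. Scale and precision.** The complete-data standard error of the difference is √[(0.23 × 0.77 + 0.15 × 0.85) / 600] = 0.0225, or 2.25 points. A 0.3-point shift is 0.13 of this and a 1-point shift is 0.44. With dropout unrelated to counts, the SD with counts divided by the SD without was 0.99 and 1.00 over 500 simulated trials. The relative Monte Carlo error of an SD is then about 1/√(2 × 500) = 3%, so no gain is shown.

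**The case against.** Treatment plus prior values of the same outcome is a coherent, pre-specified missing-at-random model, and a redundant constant does not bias it. Week 12 procedures, IGA included, are performed at discontinuation (Protocol schedule of assessments, footnote 2). Visits are assigned by study day, with Days 2 to 11 counted as Week 1 (SAP 7.7). An early leaver who attends that visit therefore has a post-baseline score, and later dropouts bring observed IGA scores that carry severity information. LOCF and missing-as-failure do not use this model. In the adverse simulated scenario, missing-as-failure gave 7.4 to 8.0 points against a true 7.9 to 8.0, so an inflated primary estimate would stand out against it. The constant-baseline rule in 6.4 also sits in a paragraph about an MCMC step that 6.2 applies only to lesion counts, so its absence from 6.2 need not be an oversight.

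Most of this stands, and it limits the size of the point. It does not put severity information back into the model. The 6.3 analysis shares the gap, 6.4 changes only how prior scores are coded, and LOCF and missing-as-failure make different assumptions, so none of them tests whether arm and prior IGA are enough.

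A reader might infer that a large share of dropouts, say 25 to 40%, will be imputed from arm alone. The documents give no such figure, and the discontinuation visit argues against it.

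**Conclusion.** The point holds as a modest weakness of the imputation model. Baseline IGA is essentially constant, baseline counts are left out, and subjects with no post-baseline score are imputed from arm alone (from vehicle in 6.3). The same applies to PGA in the ITTT population. The lesion-count imputation is not affected, because its models already include the baseline count.

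The effect on the IGA difference is nil if dropout is unrelated to baseline counts and about 0.1 to 0.3 points if it depends on them equally in both arms. It reaches roughly 0.4 to 1 point in favour of active only if dependence is strong and confined to the active arm. The correlations, dropout odds ratios and early-loss shares behind these figures are assumptions. Sample size is unaffected.

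Two stronger readings are tempting. One is that the primary result is expected to favour active by about a point. Nothing in the documents indicates count-dependent dropout in one arm only, so that figure is an extreme case. The other is that precision is lost even when dropout is unrelated to severity; the simulations do not show this.

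**What to change.** In addendum sections 6.2 and 6.3, add baseline inflammatory and non-inflammatory counts as continuous covariates at every weekly IGA/PGA step: facial counts for IGA, truncal counts for PGA. Amend the text and the example code together.

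Add the counts; do not substitute them for baseline IGA/PGA. The ITT population keeps any randomized subject with an out-of-range baseline grade (SAP 5.1 and 5.5), and that subject's success is measured from that grade. Keep the baseline score where it varies, and carry over the 6.4 rule that drops it when all subjects share one value.

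The cost is two more parameters per model. No new data collection is needed: facial counts are scheduled at Baseline, and truncal counts are omitted only for children who are outside the ITTT population.

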6.3. Multiple Imputation – Missing Not at Random

As a sensitivity analysis, the multiple imputation process will be repeated assuming that the data is missing not at random. This process will be the same as the one described for the Missing at Random analysis, but with the assumptions changed. The Missing Not at Random dataset will use data collected from vehicle subjects to impute missing observations.

Below is an example of the SAS syntax for the logistic MI for IGA/PGA for the missing not at random assumption:

```
proc mi data=transI seed=18251 out=miI1 nimpute=50 noprint;
class trt01pn baseline week_1;
var baseline week_1;
monotone logistic(week_1=baseline);
mnar model(week_1 / modelobs=(trt01pn="2"));
run;

proc mi data=miI1 seed=18251 out=miI2 nimpute=1 noprint;
by _IMPUTATION_;
class trt01pn baseline week_2;
var trt01pn baseline week_1 week_2;
monotone logistic(week_2=baseline week_1);
mnar model(week_2 / modelobs=(trt01pn="2"));
run;

proc mi data=miI2 seed=18251 out=miI3 nimpute=1 noprint;
by _IMPUTATION_;
class trt01pn baseline week_4;
var trt01pn baseline week_1 week_2 week_4;
monotone logistic(week_4=baseline week_1 week_2);
mnar model(week_4 / modelobs=(trt01pn="2"));
run;

proc mi data=miI3 seed=18251 out=miI4 nimpute=1 noprint;
by _IMPUTATION_;
class trt01pn baseline week_8;
var trt01pn baseline week_1 week_2 week_4 week_8;
monotone logistic(week_8=baseline week_1 week_2 week_4);
mnar model(week_8 / modelobs=(trt01pn="2"));
run;

proc mi data=miI4 seed=18251 out=miI(rename=(_imputation_=imp)) nimpute=1
noprint;
by _IMPUTATION_;
class trt01pn baseline week_12;
var trt01pn baseline week_1 week_2 week_4 week_8 week_12;
monotone logistic(week_12=baseline week_1 week_2 week_4 week_8);
mnar model(week_12 / modelobs=(trt01pn="2"));
run;
```

Below is an example of the SAS syntax for the MCMC and linear MI procedures for lesion counts for the missing not at random assumption:

```
proc mi data=transI seed=18251 out=mcmcI(rename=_imputation_=imp) nimpute=50
minimum=0 noprint;
mcmc impute=monotone chain=single nbiter=200 niter=100;
var baseline week_1 week_2 week_4 week_8 week_12;
run;

proc mi data=mcmcI seed=18251 out=miI nimpute=1 minimum=. 0 0 0 0 0 0
noprint;
by imp;
class trt01pn;
var baseline week_1 week_2 week_4 week_8 week_12;
monotone reg(week_12=baseline week_1 week_2 week_4 week_8);
mnar model(week_1 / modelobs=(trt01pn="2"));
mnar model(week_2 / modelobs=(trt01pn="2"));
mnar model(week_4 / modelobs=(trt01pn="2"));
mnar model(week_8 / modelobs=(trt01pn="2"));
mnar model(week_12 / modelobs=(trt01pn="2"));
run;
```

